11.1.2 SAMPLE SIZE FOR THE SECONDARY EFFECTIVENESS ENDPOINT

The first secondary effectiveness endpoint is the 12-month outcome of $\geq 20\%$ reduction in unmedicated diurnal IOP (medication washed out if applicable) from baseline. Based on P170043 and P160024, the percent of eyes achieving this outcome for the cataract surgery alone is 75.4% (89/118) and 70.1% (131/187). Therefore, the percent of cataract-surgery-alone eyes achieving this secondary effectiveness outcome is estimated as 73%. The corresponding statistical hypotheses are $H_0: P_{1\text{OMNI}} \leq 0.73$ and $H_a: P_{1\text{OMNI}} > 0.73$, where $P_{1\text{OMNI}}$ is the probability of eyes achieving the first secondary effectiveness endpoint.

The second secondary effectiveness endpoint is the 12-month outcome of unmedicated diurnal IOP (medication washed out if applicable) of ≥ 6 mmHg and ≤ 18 mmHg. Based on P170043 and P160024, the percent of eyes achieving this outcome for the cataract surgery alone is 63.6% (75/118) and 47.6% (89/187). Therefore, the percent of cataract-surgery-alone eyes achieving this secondary effectiveness outcome is estimated as 55% (approximate average of 63.6% and 47.6%). The corresponding statistical hypotheses are $H_0: P_{2\text{OMNI}} \leq 0.55$ and $H_a: P_{2\text{OMNI}} > 0.55$, where $P_{2\text{OMNI}}$ is the probability of eyes achieving the second secondary effectiveness endpoint.

The formal conclusion of the secondary effectiveness endpoints will not be determined if the primary effectiveness endpoints are not statistically significant. Meanwhile, the conclusion of the second secondary effectiveness endpoint will not be determined if the first secondary effectiveness endpoint is not statistically significant (i.e., using the step-down approach for the secondary effectiveness endpoint). Therefore the significance level is two-sided 0.05 or one-sided 0.025 for both of the secondary effectiveness endpoints.

Based on the binomial distribution with a one-sided significance level of 0.025 (or two-sided 0.05), a sample size of **105** eyes at 12 months provides a statistical power of at least 80% at a true $P_{1\text{OMNI}}$ of 0.85, and a sample size of **91** eyes at 12 month provides at least 80% at a true $P_{2\text{OMNI}}$ of 0.70. Therefore, at least **105** eyes at 12 months are needed for the secondary effectiveness endpoints.

11.1.3 SAMPLE SIZE OF THE STUDY

Based on the discussion in Section 11.1.1 and 11.1.2 the sample size for the effectiveness endpoints is **130** eyes treated with the study device with the cataract surgery.

With a sample size of 130 eyes, there is a probability of 95% to observe at least one incidence of a safety event with an event rate of about 2.4%.

In May of 2019, the study protocol was revised to require at least one ocular hypotensive medication at the screening for the study eyes. Since the study has treated

some eyes that did not have ocular hypotensive medications at screening, the planned sample size of the study is increased to approximately 145 eyes.

11.2 ANALYSIS POPULATIONS

The intent-to-treat (ITT) analysis population includes all subjects who are enrolled and treated, regardless of whether or not they have a protocol deviation. Due to the eligibility revision in May of 2019 on requiring at least one ocular hypotensive medication, the modified ITT (mITT) population includes all ITT except for the treated eyes that were not on any ocular hypotensive medication at the screening visit. The per-protocol analysis population (PP) is a subset of mITT, which includes all subjects who have taken at least one ocular hypotensive medication at screening and have uneventful cataract extraction followed by ab-interno transluminal viscoelastic delivery and trabeculotomy, 12 month IOP and medication data, and have no clinically significant protocol deviations. It should be noted that the mITT subjects with an uneventful study procedure but with SSIs before the 12-month visit will be included in the PP population even if they do not have the 12-month IOP and medication data. The primary analyses on the primary and secondary endpoint analyses will be carried out on the per-protocol population.

The safety data will be summarized based on the ITT population. The primary and secondary endpoint analyses will also be performed on the mITT population.

The data will be listed separately for the enrolled subjects that are not treated with OMNI and treated subjects that do not have ocular hypotensive medications at the screening.

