9 STUDY PROCEDURES

9.1 STUDY SCHEDULE

Table 1: Study Visit Schedule

Note: The fellow eye should be followed per the PI's usual practice based on the ocular health of the fellow eye.

PROCEDURE	SCREENING (DAY -45 TO -6)	BASELINE (DAY -7 TO 0)	SURGERY (DAY 0)	1 DAY (DAY 1)	1 Wk (DAY 5-9)	1 M (DAY 21-35)	3 M (DAY 70-98)	6 M (DAY 150-210)	12 M (DAY 330-420)	12 M WASHOUT ²⁹ (DAY 330-420)
Informed Consent	X									
Demographics	X									
Medical & Ocular History	X	X								
Medication Log	X	X	X	X	X	X	X	X	X	X
BCVA (ETDRS), with manifest refraction	X	X			X	X	X	X	X	
Visual Field (Humphrey 24-2 SITA)	X									X
IOP (Goldmann)	X			X	X	X	X	X	X ³⁰	
Unmedicated diurnal IOP (Goldmann)		X							X ³¹	X
Slit Lamp Exam	X	X		X	X	X	X	X	X	
Gonioscopy	X				X	X	X	X	X	
Dilated Fundus Exam/C:D Ratio	X								X	
Eligibility Assessment	X	X								
Cataract Extraction + ab-interno transluminal viscoelastic delivery and trabeculotomy			X							
AE Assessment	X	X	X	X	X	X	X	X	X	X

²⁹ The 12 month washout visit is only required for subjects who are taking hypotensive medications at the 12 month visit.

³⁰ This is only required for subjects who are taking hypotensive medications at the 12 month visit.

³¹ If subject is not on any hypotensive medications, a diurnal IOP measurement should be obtained at the 12 month visit as unmedicated IOP.

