9.8 FOLLOW-UP VISITS

Follow-up visits should be performed according to the schedule provided in Table 1 (page 17). All attempts should be made to conduct each follow-up visit within the time interval specified in Table 1. Evaluations conducted outside the prescribed time period will be considered protocol deviations.

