11 STATISTICAL CONSIDERATIONS

11.1 HYPOTHESES AND SAMPLE SIZE CALCULATION

11.1.1 SAMPLE SIZE FOR THE PRIMARY EFFECTIVENESS ENDPOINTS

First Primary Effectiveness Endpoint

The first primary effectiveness endpoint is the reduction in the unmedicated diurnal IOP from baseline to 12 months postoperatively. The study objective is to show that the mean unmedicated diurnal IOP reduction of the study treatment (i.e. ab-interno transluminal viscoelastic delivery and trabeculotomy performed with OMNI system performed after uneventful cataract extraction) is superior to that of the cataract extraction alone. Based on recent approved MIGS studies, the mean \pm SD unmedicated diurnal IOP reduction at 12 months for the cataract extraction alone is 6.7 mmHg \pm 3.6 mmHg (N = 118) for Glaukos P170043 and 6.3 mmHg \pm 4.0 mmHg (N = 187) for Ivantis P160024. Therefore, the mean \pm SD unmedicated diurnal IOP reduction at 12 months for the cataract extraction alone is estimated as 6.5 mmHg \pm 3.8 mmHg.

The corresponding statistical hypotheses are as follows:

$H_0: \mu_{OMNI} \leq 6.5$ mmHg and $H_a: \mu_{OMNI} > 6.5$ mmHg, where μ_{OMNI} is the mean unmedicated diurnal IOP reduction at 12 months for the OMNI Surgical System in combination with Cataract Extraction.

Based on a one-sample t-test with a one-sided significance level of 0.025 (or two-sided 0.05), a sample size of 116 eyes at 12 months provides a statistical power of 80% at a true μ_{OMNI} of 7.5 mmHg.

Second Primary Effectiveness Endpoint

The second primary effectiveness endpoint is the reduction in the number of IOP-lowering medications from screening to 12 months (before medications washed out if applicable) postoperatively.

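### One per-protocol set for both co-primaries can discard a recorded 12-month drug count because the unmedicated IOP is missing, which probably, but not certainly, favours the medication test

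*Combined protocol and SAP*

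**What the plan says.** All references are to the combined protocol and SAP.

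- **PP membership (11.2).** One PP set is defined as a subset of mITT. Besides screening drug use and an uneventful procedure, it requires "12 month IOP and medication data, and have no clinically significant protocol deviations". The only exception to the data rule is for eyes with a secondary surgical intervention (SSI) before month 12, which "will be included in the PP population even if they do not have the 12-month IOP and medication data".
- **Role of PP (11.2, repeated in 11.4).** "The primary analyses on the primary and secondary endpoint analyses will be carried out on the per-protocol population". The same analyses are also run on mITT.
- **Medication endpoint (11.1.1).** The reduction is counted "from screening to 12 months (before medications washed out if applicable) postoperatively".
- **IOP endpoints (7.1).** The IOP co-primary and both secondaries use the unmedicated diurnal IOP.
- **Who needs a further visit (9.1, Table 1 footnotes).** For eyes on drops: "The 12 month washout visit is only required for subjects who are taking hypotensive medications at the 12 month visit". For eyes off drops: "If subject is not on any hypotensive medications, a diurnal IOP measurement should be obtained at the 12 month visit as unmedicated IOP". Another footnote requires an ordinary Goldmann IOP at month 12 for eyes on drops.

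**The concern.** The medication outcome is complete once the 12-month visit is done. Whether it enters the primary test may nevertheless depend on a different measurement. For an eye still on drops, that measurement exists only if the subject stops the drops and returns. For a drug-free eye, it is taken at the 12-month visit itself.

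So on the natural reading, membership of the medication analysis depends partly on the medication outcome. The test would describe eyes that are drug-free or that completed washout, whereas the objective concerns treated eyes in general. This differs from the missing-data problem in the IOP endpoint. There the value does not exist; here it is in the database and goes unused.

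The planning distance is short: the goal is a mean reduction of 0.75 drugs and the assumed truth is 1.0. A small upward shift therefore matters. Both co-primaries must succeed for the study claim, and the secondaries are gated on them.

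**Working it through.** **Plan's own figures.** One-sample t-test, exact noncentral t, one-sided 0.025, 80% power.

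- IOP co-primary, difference 1.0 mmHg, SD 3.8: 116 eyes, as stated. Allowing for 10% drop-out, 116/0.9 = 129, consistent with about 130.
- Medication co-primary, difference 0.25, SD 1.0: 128 eyes. The stated 101 is what one-sided 0.05 would give. Power with 116 eyes is 76.1%. This is a separate matter and is not used below, but that test has no spare power.

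**Side-by-side check at month 12.**

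| Eye at month 12 | Drug count recorded | Unmedicated diurnal IOP | In PP (natural reading) |
|---|---|---|---|
| Off drops, full diurnal series | yes | same visit | yes |
| Off drops, incomplete series | yes | missing | no |
| On drops, washout completed | yes | washout visit | yes |
| On drops, washout missed | yes | missing | no |

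Some washout losses follow from the schedule. The 12-month and washout visits share days 330–420, and many agents in Table 2 have a 28-day minimum. Since 420 − 28 = 392, an eye on such an agent seen after day 392 cannot finish in the window if washout starts at that visit. Section 9.8 adds: "Evaluations conducted outside the prescribed time period will be considered protocol deviations". These passages need reconciling with 11.2, which does not define a clinically significant deviation.

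**Size, simple formula.** Let x be the share of eyes removed and g the amount by which their mean reduction lies below the overall mean. Then bias = x·g/(1 − x). The plan gives neither quantity. Assumed: 30–50% of eyes on drops, g = 0.6–1.0.

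- 10% miss washout, low end: x = 0.3 × 0.1 = 0.03, bias = 0.03 × 0.6/0.97 = +0.019.
- 10% miss, central: x = 0.4 × 0.1 = 0.04, bias = 0.04 × 0.8/0.96 = +0.033, which is 13% of 0.25.
- 10% miss, high end: x = 0.5 × 0.1 = 0.05, bias = 0.05 × 1.0/0.95 = +0.053.
- 20% miss, high end: x = 0.10, bias = 0.10 × 1.0/0.90 = +0.111, which is 44% of 0.25.

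With normal data, SD 1.0, 116 eyes and a true mean of 0.75, a bias of 0.033 takes the one-sided error from 2.5% to 5.4%. A bias of 0.07 takes it to 11.3%.

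**Size, drug-count simulation.** Nine assumed scenarios with 116 eyes, 40,000 runs and a true mean of 0.75. Screening counts run from 1 to 4. Eyes end drug-free, one drug lower or unchanged. In these scenarios 53–87% of eyes remain on drops.

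| On-drop eyes missing washout | Eyes lost | PP mean | One-sided error |
|---|---|---|---|
| 0% | 0 | 0.750 | 1.4–1.6% |
| 10% | about 6–10 | 0.776–0.806 | 2.8–4.8% |
| 20% | about 12–20 | 0.807–0.872 | 5.4–11.8% |

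The skewed counts start below the nominal 2.5%, so the final level is lower than under the normal model for a similar shift.

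**Direction.** Every eye lost through washout is on at least one drug, so its reduction is at most 0 if it started on 1, and at most 1 if it started on 2. An eye going from 4 to 1 has a reduction of 3. In the normal model with 6 of 116 eyes removed:

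- removed eyes average 0: mean (87 − 0)/110 = 0.791, error 6.2%;
- removed eyes average 0.5: mean (87 − 3)/110 = 0.764, error 3.5%;
- removed eyes average 1.0: mean (87 − 6)/110 = 0.736, error 1.8%, so the bias reverses.

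**Offset from drug-free eyes.** In the central case drug-free eyes lie 0.4 × 0.8/0.6 = 0.533 above the overall mean. If 5% of them lack a full diurnal series, the bias is (0.36 × −0.8 + 0.57 × 0.533)/0.93 = +0.017. If 10% do, it is (0.36 × −0.8 + 0.54 × 0.533)/0.90 = 0.

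**The case against.** The strongest objection is textual. Section 11.2 says only 12-month IOP and does not use the fuller term given for the endpoint. Table 1 takes a Goldmann IOP at month 12 precisely in eyes on drops. Read literally, such an eye has both data items and stays in PP without washout. This stands as a possible reading. It does not remove the point, because every primary and secondary IOP endpoint is the unmedicated diurnal value, and a plan that leaves membership of its primary set open to two readings needs a sentence either way.

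A reader might infer that the rule certainly biases the test towards success, because the removed eyes have the smallest reductions and drug-free eyes can never be lost. The documents do not support that. Eyes enter on 1–4 drugs, so a removed eye may have a larger reduction than a retained one. A drug-free eye can also lose its IOP value, since the diurnal mean needs three timed readings (20.5). Washout is the heavier demand, so an upward shift remains the likelier outcome.

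Several safeguards are real. A failed washout may be repeated within the window (9.5), only clinically significant deviations exclude an eye, and SSI eyes are kept. The IOP co-primary must also succeed, so the medication test alone cannot carry the study. The mITT analysis can use the recorded count and would expose a gap. It is supportive, however, and does not replace the primary test.

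**Conclusion.** The point holds in conditional form. On the natural reading of 11.2, a recorded co-primary outcome is discarded when a different measurement is missing, and this happens mainly to eyes still on drops.

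The probable effect is an upward shift in the mean drug reduction. If about 10% of on-drop eyes miss washout, the shift is roughly +0.02 to +0.05 drugs against a planning distance of 0.25, with one-sided error of about 3–5% in the drug-count model. At 20% the simulated error is 5.4–11.8%. With only a few losses the change is a point or two.

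These figures rest on assumed shares on drops, washout losses and reductions in the lost eyes, and they exclude any offset from drug-free eyes. It would go too far to say that the error rate is shown to exceed 0.025. What the documents do show is that nothing in 11.2 prevents it. The change is worth making because it removes the dependence in both directions.

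**What to change.** In 11.2, make the data requirement endpoint-specific:

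- **Medication co-primary.** PP includes every otherwise eligible mITT eye with a recorded 12-month pre-washout drug count, whether or not a 12-month unmedicated diurnal IOP exists. A missed or incomplete washout or diurnal series does not by itself exclude the eye from this test.
- **IOP co-primary and both secondaries.** PP requires the 12-month unmedicated diurnal IOP, named as such.
- **SSI exception.** Keep it as written.

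This takes a sentence or two and no new visits or data. The number of eyes may differ slightly between the two co-primaries, so each should be reported with its own denominator. The medication result may be slightly less favourable.

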11.3 DEMOGRAPHICS AND BASELINE CHARACTERISTICS

Demographic variables gender, race, ethnicity, and age will be summarized for all enrolled subjects treated with OMNI Surgical System, along with medical history. Descriptive statistical summaries of pre-treatment parameters (min, max, median, mean, standard deviation) will also be provided. The same analyses will be performed for the mITT and PP populations.

11.4 EFFECTIVENESS ENDPOINTS AND ANALYSIS METHODS

Descriptive statistics on continuous variables will include mean, standard deviation, median, minimum, and maximum. Confidence intervals for change from baseline will be included for selected endpoints. Categorical variables will be summarized using frequency counts and percentages. Exact confidence intervals for point estimates may be provided. Statistical testing will be one-sided with a significance level of 0.025 or two-sided significance level of 0.05) unless specify otherwise. Data listings of individual subject data may be provided.

As described above, the primary analyses of the primary and secondary effectiveness endpoints will be based on the PP population (Section 11.2), although the analyses will also be performed on the mITT population. The safety data will be summarized based on the ITT population.

11.4.1 PRIMARY EFFECTIVENESS ENDPOINTS

The IOP reduction from baseline to 12 months postoperatively and the reduction in number of IOP-lowering medications from baseline to 12 months will be calculated for each eye and summarized descriptively. The 95% confidence interval of the mean reduction will be derived based on the t-distribution. The one-sample t-test will be performed for testing the statistical hypotheses described in Section 11.1.1. It should be noted that, for eyes with secondary surgical interventions (SSI) to control IOP or with SSI that can affect the IOP before 12 months, the last available observed data before the SSI will be used to impute the 12-month data. For the analyses based on the mITT population, the following imputation for subjects with missing 12-month data but without SSI may be performed:

- The within-eye worst IOP (collected after 3 months postoperatively or IOP at baseline for the subjects with no data after postoperative 3 months) for the missing 12-month IOP and worst number of IOP lowering medications (collected after 3 months postoperatively or IOP-lowering medication data at baseline for the subjects with no data after postoperative 3 months) for the missing 12-month number of IOP-lowering medications.
- The worst IOP (collected after 3 months postoperatively or IOP at baseline for the subjects with no data after postoperative 3 months) during the study for the missing 12-month IOP and worst number of IOP-lowering medications (collected after 3 months postoperatively or IOP-lowering medication data at baseline for the subjects with no data after postoperative 3 months) during the study for the missing 12-month number of IOP-lowering medications.
- The mean IOP during the study for the missing 12-month IOP and mean number of IOP-lowering medications during the study for the missing 12-month number of IOP-lowering medications.
- The last-observed-carry-forward approach.

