7 STUDY ENDPOINTS

7.1 EFFECTIVENESS ENDPOINTS

The **Primary effectiveness endpoints** are:

- Reduction in mean unmedicated diurnal IOP from baseline to 12 months; and
- Reduction in mean number of IOP-lowering medications from screening to 12 months

The **Secondary effectiveness endpoints** are:

- Percent of eyes with a $\geq 20\%$ reduction in unmedicated diurnal IOP at 12 months
- Percent of eyes with unmedicated diurnal IOP between 6 and 18 mmHg inclusive at 12 months

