8 STUDY SELECTION CRITERIA

8.1 INCLUSION CRITERIA

For inclusion in this study, subjects must meet all the following criteria (only one eye of each subject is eligible, and all ocular criteria apply to the study eye only unless otherwise indicated):

1. Male or female subjects, 22 years or older
2. Visually significant cataract
3. Diagnosed with mild to moderate open angle glaucoma (e.g. primary open angle glaucoma, pigmentary glaucoma, pseudoexfoliative glaucoma) as documented in subjects' medical record per ICD-10 guidelines
4. At screening, a medicated IOP \leq 33 mmHg and on 1-4 IOP-lowering medications with a stable medication regimen for two months prior to screening visit²⁸
5. At baseline, unmedicated diurnal IOP 21-36 mmHg and IOP at least 3 mmHg higher than screening IOP
6. Scheduled for cataract extraction followed by ab-interno transluminal viscoelastic delivery and trabeculotomy using the OMNI Surgical System
7. Shaffer grade of \geq III in all four quadrants
8. Potential of good best corrected visual acuity post cataract extraction, in the investigator's judgment
9. Able and willing to comply with the protocol, including all follow-up visits
10. Understands and signs the informed consent.

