9.5 WASHOUT OF HYPOTENSIVE MEDICATIONS

Subjects who meet all screening eligibility criteria will be instructed to discontinue their ocular hypotensive medication regimen in the study eye only, and to return for a Baseline visit after completing the appropriate washout period. Glaucoma medication discontinuation can be staged (for patients on multiple medications) so that the pressure increase duration is minimized to the greatest possible extent during the washout period. For example, if a patient is on a prostaglandin (PGA) and a Carbonic Anhydrase Inhibitor (CAI), the PGA could be discontinued 4 weeks prior to the Baseline visit but the allowed to continue until 5 days before Baseline.

If the study subject fails to remember to not use ocular hypotensive medication for the study eye per the required washout period, they can be re instructed to washout and return for the Baseline or 12-month washout IOP visit as long as it falls within the specified visit window.

The minimum wash-out periods are specified in Table 2 below. Note: The maximum washout period is 6 weeks. Therefore, if the study procedure cannot be scheduled within one week of the end of the washout period, the subject should be restarted on glaucoma medication until the Day 0 visit (but after the washed-out diurnal IOP has been obtained).

Table 2: Ocular Hypotensive Medication Washout Periods

Brand Name/Chemical Name	Minimum washout period
Carbonic Anhydrase Inhibitors	
Diamox® (Acetazolamide) – oral Rx	5 days
Neptazane® (Methazolamide) – oral Rx	5 days
Azopt® (Brinzolamide)	5 days
Trusopt® (Dorzolamide Hydrochloride)	5 days
Muscarinic Agonists	
Salagen, Pilocar (Pilocarpine)	5 days
Alpha Adrenergic Agonist	
Alphagan® (Brimonidine)	14 days
Iopidine® (Apraclonidine Hydrochloride)	14 days
Beta Blockers	
Betagan® (Levobunolol Hydrochloride)	28 days
Betoptic® (Betaxolol Hydrochloride)	28 days
OptiPranolol® (Metipranolol)	28 days
Timoptic/Betimol® (Timolol Maleate)	28 days
Prostaglandin Analogs	
Lumigan® (Bimatoprost)	28 days
Travatan® (Travoprost)	28 days
Xalatan® (Latanoprost)	28 days
Zioptan® (Tafluprost)	28 days
Vyzulta® (Latanoprostene Bunod)	28 days
Rho Kinase Inhibitor	
Rhopressa® (Netarsudil)	28 days
Combined Medications	
Combigan® (Brimonidine Tartrate/Timolol Maleate)	28 days
Cosopt® (Dorzolamide Hydrochloride/ Timolol Maleate)	28 days
Simbrinza® (Brinzolamide/Brimonidine Tartrate)	28 days
Other	Contact Sponsor

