11.4.3 COVARIATE ANALYSIS

The following variables will be examined for their prognostic value to the primary and secondary effectiveness endpoints using the PP population with the imputation used for the IOP-related SSIs:

- Age group (based on observed quartiles)
- Gender (male and female)
- Race (White and non-White)
- Ethnicity
- Baseline IOP group (based on observed quartiles)
- Screening Number of IOP-lowering medications (1, 2, 3 and 4)
- Study site

For the primary effectiveness endpoints, one-way ANOVA with one of the factors listed above will be used to check the possible covariate effects. For the secondary effectiveness endpoint, Fisher's test will be performed. A p-value of 0.15 will be used for evaluating the possible covariate effects.

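### Section 11.4.1 measures the medication co-primary, and its worst-case fallback, from baseline, when the study eye is washed out; the endpoint is defined from screening

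*Combined protocol and SAP*

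**What the plan says.** The synopsis and Section 7.1 define the second co-primary as "Reduction in mean number of IOP-lowering medications from screening to 12 months". Section 11.1.1 builds its hypotheses on the same definition and takes the 12-month count before any washout. The covariate list in Section 11.4.3 and the interim endpoints in Section 11.6 also use the screening count.

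Section 11.4.1, the operative analysis rule, says instead that "the reduction in number of IOP-lowering medications from baseline to 12 months will be calculated for each eye". Its first two mITT imputation options, both described as worst values, fall back on "IOP-lowering medication data at baseline for the subjects with no data after postoperative 3 months". Section 11.4.4 stratifies two 12-month IOP distributions by medication change from baseline.

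Screening and Baseline are separate visits in Table 1. Between them, Section 9.5 has the subject stop hypotensive medication in the study eye and "to return for a Baseline visit after completing the appropriate washout period". Inclusion criterion 5 confirms the state of the eye at that visit: "At baseline, unmedicated diurnal IOP 21-36 mmHg and IOP at least 3 mmHg higher than screening IOP". At screening, criterion 4 requires 1 to 4 medications.

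**The concern.** One of the two co-primaries has a derivation rule that conflicts with its own definition, and both co-primaries must succeed. In the first sentence of Section 11.4.1, baseline must mean the washed-out visit for IOP but an earlier visit for medications if the test is to make sense. No section says so. The Medication Log is completed at both visits, so a Baseline-visit record exists and a programmer could use it.

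There are two consequences. Followed literally, the rule makes the medication hypothesis impossible to prove, in the per-protocol analysis as well; that error would show itself at once. If someone corrects only the sentence on the reduction, the error left in the fallback runs the other way. A rule meant to be pessimistic could then assign the most favourable possible value, and nothing in the output would look odd.

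**Working it through.** **Inputs from the documents.** Null bound 0.75 (control mean 1.0 less a margin of 0.25), SD 1.0, one-sample t-test at one-sided 0.025, about 10% dropout and 130 treated eyes (Section 11.1.1); 1 to 4 medications at screening (Section 8.1).

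**The plan's own figure.** Section 11.1.1 gives 101 eyes for 80% power at a true mean of 1.0. With the inputs above, the non-central t distribution gives 70.1% power at 101 eyes and needs 128 for 80%. The figure of 101 matches one-sided 0.05 (80.2%). That is a separate matter; nothing below depends on it.

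**Step 1: literal reading.** Count at the Baseline visit = 0 in a compliant eye. Reduction = 0 − (12-month count) ≤ 0 for every such eye, so the mean cannot exceed 0.75. Example with an assumed screening mean of 2.0 and a 12-month mean of 1.0: from screening the reduction is 2.0 − 1.0 = +1.0; from the washed-out visit it is 0 − 1.0 = −1.0. Likewise, no compliant eye could appear in Section 11.4.4 with a medication decrease.

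**Step 2: an mITT eye with no SSI and no data after month 3.** Let c be its screening count.

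| Reference for the reduction | Fallback for the 12-month count | Imputed reduction |
|---|---|---|
| Screening | Screening | c − c = 0 |
| Washed-out visit | Washed-out visit | 0 − 0 = 0 |
| Screening | Washed-out visit | c − 0 = c |

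Only the third row, the half-corrected text, favours the device. The parallel IOP fallback gives such an eye zero reduction.

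**Step 3: size of the third row.** The documents give neither the mean screening count nor the share of eyes f that would use the fallback. Assumptions: mean c of 1.5 to 2; f of 2%, 5% or 10%; n = 130; SD 1.0; true mean exactly 0.75, shared by the missing eyes.

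- Gap between the screening and washed-out fallbacks = f × c
- Bias, washed-out fallback = f × (c − 0.75)
- Bias, screening fallback = −0.75 × f
- Rejection probability: non-central t, 129 df, non-centrality = bias × √130

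Example, f = 5%, c = 2: bias = 0.05 × 1.25 = 0.0625; non-centrality = 0.0625 × 11.40 = 0.713; rejection probability 10.5%.

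| f | Gap (c = 1.5 / 2) | Bias, washed-out (c = 1.5 / 2) | One-sided error, washed-out (c = 1.5 / 2) | One-sided error, screening fallback |
|---|---|---|---|---|
| 2% | 0.03 / 0.04 | 0.015 / 0.025 | 3.7% / 4.7% | 1.7% |
| 5% | 0.075 / 0.10 | 0.0375 / 0.0625 | 6.2% / 10.5% | 0.9% |
| 10% | 0.15 / 0.20 | 0.075 / 0.125 | 13.3% / 29.3% | about 0.25% |

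A simulation (40,000 runs, with 3, 6 or 13 of the 130 eyes set to c) gave 3.9% / 4.7%, 5.8% / 8.9% and 13.4% / 27.3%. The middle row is slightly lower partly because 6 eyes is less than 5% of 130.

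**The case against.** The strongest reply is that the documents already settle the main calculation. Section 11.4.1 sends the t-test to the Section 11.1.1 hypotheses, which start from screening. The plan also uses baseline loosely elsewhere: Sections 9.4 and 20.6 let a pre-visit field serve as the baseline field although Table 1 schedules it at Screening, and Section 20.7 records the fundus examination on a Baseline form although Table 1 has none at that visit. The likeliest meaning is the preoperative regimen, and a result that could never succeed would be noticed. This stands as a reading of intent. It does not make the text consistent, because baseline medications are nowhere defined as the screening count.

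The second reply is that the inflated error rates need baseline to mean two different visits within one section. This also stands: under either consistent reading the fallback eye scores zero and there is no inflation. The table describes a half-corrected text only.

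Third, the fallback has limited reach. The primary analysis is per protocol ("The primary analyses on the primary and secondary endpoint analyses will be carried out on the per-protocol population"). The imputations are optional and mITT only, eyes with SSI follow a separate rule, and two of the four options are affected. The second of these might mean a study-wide worst value, which would dilute the effect, although its text still refers to baseline data. The 10% row needs every planned dropout to lack data after month 3 despite a scheduled 6-month visit, so it is an upper end.

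**Conclusion.** The concern holds. As written, the derivation rule for the medication co-primary contradicts its definition, and followed literally it gives a result that cannot pass. This part needs no assumption beyond compliance with the washout, and it reaches the per-protocol analysis. It is most likely a drafting slip, not a change of endpoint.

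The fallback effect is conditional: it requires the reduction to be taken from screening while the fallback stays at the washed-out visit. In that case the choice of fallback moves the mean reduction by 0.03 to 0.20 medication, against a margin of 0.25. The error rates in the table are those of one optional supportive analysis of one endpoint, not of the trial's overall decision. The wording conflict is certain; the size of the bias depends on the assumed screening count and missing share. The text should be corrected before the analysis is programmed.

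**What to change.** In Section 11.4.1, state the medication reduction as running from screening to 12 months. In both worst-value imputation options, make the medication fallback the number of IOP-lowering medications at screening, which gives such an eye zero reduction. Keep baseline for IOP throughout. In Section 11.4.4, define medication change from screening in both stratified distributions. Make all these edits together, since correcting only the first creates the favourable fallback.

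The cost is a few words in two sections and no new data, since Section 9.4 already requires the medication count to be collected at the Screening visit. The per-protocol result does not change if it was going to be computed from screening. The mITT medication result under the worst-value imputations may be slightly less favourable than under a washed-out fallback.
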